cognitive behavioral therapy and includes mindfulness exercises, promotion of behavioral activation through pleasant activities and developing supportive relationships. The intervention is led by CHWs and organized into 10 sessions, tailored to the participant using a collaborative approach, to improve mood symptoms, augment self-reported functioning, and increase self-reported quality of care among participants with moderate to severe symptoms of depression and/or anxiety. The Strong Minds-Strong Communities intervention seeks to increase engagement, decrease depression and anxiety symptoms, improve functioning, and increase perceived quality of care among low-income racial/ethnic and linguistic minorities. The 10-session intervention is culturally adapted for use among a wide group of minority populations (Latino, Asian, African-American and Afro Caribbean), has few exclusionary criteria to improve generalizability, and is administered by CHWs from within the partner ACOs as opposed to Masters or PhD-level clinicians. The CHW will conduct a welcome visit with eligible participants, introduce them to the program, and provide the workbook and educational materials. The CHW will give feedback on symptoms to the treating primary care provider (PCP) if participants allow it and will use motivational interviewing techniques to increase engagement. The first 5 sessions will occur weekly. Every other week, the CHW will evaluate the participant with either the PROMIS for depression or for anxiety (short form), the 9th question from the PHQ-9 regarding suicidality, and if necessary, the 5-item suicide questionnaire, both for participant safety and to ensure the participant's mental health is not deteriorating to the point where immediate intervention or referral is necessary. This symptom assessment will be done for both intervention and enhanced usual care groups). Sessions will continue until at least 8-10 are completed or 6 months have passed.

The Strong Minds-Strong Communities intervention is complemented by a care manager that links participants to services for needs related to social determinants of health (i.e. education,

housing). The Strong Minds-Strong Communities intervention will be compared with an enhanced usual care group.

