Participants can complete the intervention by telephone and/or during off hours (evenings, weekends) to facilitate participation. If we find participants are too severely impaired to benefit (see exclusion criteria), we will link them to mental health or substance abuse services and resources via the care manager.

We will offer a 'flexible approach' option. If someone is eligible after the screener but reports not being interested in participating in the study, we will ask permission to contact them 3 more times within a 6 month period (2 months after the first screening interview, 4 months and 6 months after). If they agree, we would contact them every 2 months to rescreen them and try to enroll them into the trial. 6 months after the first screening interview (after 3 calls), if the person still reports not being interested in participating, we will assume the case to be a decline to enroll, and not contact him/her again. If, after the first screening interview the person who is not interested in being enrolled asks the RA not to continue to contact them, we will also mark the case as declining to enroll.

Participants in the enhanced usual care group will receive an NIH booklet about anxiety and depression in Spanish, English, or Mandarin/Cantonese. The Care Manager will call the participant 4 times over the course of 6 months to administer the PROMIS, the 5-item suicide questionnaire, and a question about medication side effects to mimic the administration schedule in the intervention group, with data entered in Dimagi CommCare. With the participant's permission, the care manager will inform the PCP about screening and other assessments and determine if participants should be referred to mental health or substance services and removed from control group given severity (PHQ-9 ≥ 20 , GAD-7 ≥ 15 and Paykel

=4 or 5 or active substance use). This will be considered a positive outcome for participant safety.

All enrolled participants (intervention and usual care) will be contacted for assessments over the course of 12 months: baseline, and 3-month, 6-month, and 12-month follow-ups.

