The target sample size was designed to achieve adequate power for our research questions. Using data from prior studies on the effectiveness of similar interventions, the estimated effect size for the outcomes ranged from 0·24 to 0·68. The nonparticipation rate of enrolled participants was assumed to be 13%. Our sample size of 1,200 (600 treatment and 600 control) from North Carolina and Massachusetts is thus effectively 1044. This sample yielded 87% power to detect an intervention effect size of 0·20, with a two-sided significance level of 0·05. Testing whether there is a differential effect of Strong Minds-Strong Communities based on participants' race and ethnicity means trying to determine whether race and ethnicity moderated the impact of the intervention. The racial and ethnic composition of our sample was roughly 63% Latinx, 14% non-Latinx Black, 13% Asian, 9% White, and 1% other races or ethnicities. Assuming a large effect size of the intervention for White participants ($> 0\cdot5$), a small effect size for Black participants ($< 0\cdot3$), and a medium effect size for Asian and Latinx participants ($> 0\cdot3$ and $< 0\cdot5$), we will have 80% power to detect a significant intervention effect in each racial and ethnic group with a sample size of 1044. Similarly, testing whether there is a differential effect of Strong Minds-Strong Communities in North Carolina compared to Massachusetts means testing whether site moderated the impact of the intervention.

VIII. Risks and Discomforts

A. Psychosocial (non-medical) risks:

The safety of intervention participants will be closely monitored during the Strong Minds-Strong Communities intervention. Participants will be administered the PHQ-9 depression screener and the GAD-7 anxiety screener during research interviews and biweekly during intervention sessions, and in biweekly check-ins for usual care participants. If participants endorse the Item

9 suicidality question of the PHQ-9, they will be administered the Paykel Suicidality Screener.

Those who endorse questions 4 and 5 of the Paykel, suggesting active suicidality, will be provided emergency care following emergency protocol developed by the research team.

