In the event that a participant endorses Items 4 and 5 of the Paykel Suicidality Screener (see above), the CHW or CRC administering the assessment will follow the Emergency Protocol. The protocol calls for an assessment by the local emergency services. The research team member will follow up with the participant within 24 hours. If the person is admitted to emergency psychiatric services, the research team member will follow up with the participant after 30 days. If the participant no longer reports suicidality, he/she will be allowed to continue to the study. In no case will a participant with elevated symptoms be removed from the study without ensuring an appropriate referral. If a participant scores in the severe range on the PHQ-9 or the GAD-7 (corresponding to scores of greater or equal to 20 on the PHQ-9 or greater or equal to 15 on the GAD-7) for two or more assessments, that participant will be monitored closely and the CHW's supervisor will determine whether that individual should be referred to specialty treatment. Depending on the nature of the treatment, the participant may be allowed to continue with the study. The following criteria will be used to remove a subject from the study. The participant's primary care provider will be notified if his/her symptom assessment scores remain in the severe range.

IX. Potential Benefits

A. Potential benefits to participating individuals

In terms of efficacy, it is hoped that this intervention will contribute to reduced depression and/or anxiety among a significant proportion of study participants. Depressive and anxiety symptoms from baseline will be measured by the Hopkins Symptom Checklist-25, the PHQ-9, and the GAD-7, and disability days as measured by the WHO-DAS 2.

B. Potential benefits to society (e.g. increased understanding of disease process, etc.)

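### Removal from the study for post-randomisation severity is not reconciled with assessing everyone to 12 months; if it stops assessments, the effect estimate can be biased

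*Combined protocol and SAP*

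**What the plan says.** **Section VI (Research Procedures - Intervention).** For usual care, the care manager may "determine if participants should be referred to mental health or substance services and removed from control group given severity". The listed criteria are PHQ-9 of 20 or more, GAD-7 of 15 or more, and Paykel 4 or 5 or active substance use. The section then states, without exception: "All enrolled participants (intervention and usual care) will be contacted for assessments over the course of 12 months".

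**Section VIII.A (Psychosocial risks).** This text is not limited to one arm.
- "In no case will a participant with elevated symptoms be removed from the study without ensuring an appropriate referral".
- After emergency psychiatric admission and a check at 30 days: "If the participant no longer reports suicidality, he/she will be allowed to continue to the study".
- After two or more severe PHQ-9 or GAD-7 scores, a supervisor decides on specialty referral, and then: "Depending on the nature of the treatment, the participant may be allowed to continue with the study".

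**Frequency of symptom checks.** In the intervention arm: "Every other week, the CHW will evaluate the participant". In usual care: "The Care Manager will call the participant 4 times over the course of 6 months". Section VIII.A instead gives the schedule as "biweekly during intervention sessions, and in biweekly check-ins for usual care participants", and section VI also says that the symptom assessment is done in both groups.

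**Section VII.** The model codes arm as randomised. Section VII.B imputes a missing outcome from arm, baseline score, site and baseline variables associated with missingness.

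**The concern.** Permission to continue in the study means something only if some participants do not continue. Section VIII.A therefore allows a participant to leave because of severity seen after randomisation, whereas section VI says that everyone is assessed to month 12. The plan does not say which wording governs, or whether leaving ends the outcome interviews.

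If it does, the people lost are those doing worst. The imputation model contains nothing measured after baseline, so a removed participant would be imputed as a typical person with the same arm and baseline score. Coding arm as randomised does not recover outcomes that were never collected, and section VII.B plans no sensitivity analysis for departures from missing at random. Unequal loss between the arms would then carry straight into the treatment contrast.

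**Working it through.** **Inputs from the plan (section VII.C).** 1,200 randomised, 13% nonparticipation, effect 0.20, two-sided 0.05, stated power 87%.

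**The plan's own figure.** 1,200 x 0.87 = 1,044, as stated. Unadjusted SE = 2/sqrt(1,044) = 0.0619; 0.20/0.0619 = 3.23; power = Phi(3.23 - 1.96) = 89.8%. The stated 87% is slightly conservative, and this point does not depend on it.

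**Assumptions (not in the documents).**
- Baseline correlates 0.5 with both interim severity and the month 6 score.
- Interim severity correlates r = 0.5, 0.6 or 0.7 with month 6.
- The effect applies at both the interim and month 6.
- Everyone above an arm's severity cut is lost, which is a worst case.
- Removal rates are illustrative. Of 522 per arm, 2% is about 10 people and 5% about 26.

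**Adjusted precision.** SE = sqrt(1 - 0.5^2) x 2/sqrt(1,044) = 0.0536. Full-data power for 0.20 is Phi(3.73 - 1.96) = 96.2%.

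**Bias formula.** If the top fraction p of an arm is lost, mean interim severity among those kept falls by L(p) = phi(z_p)/(1 - p). The mean outcome falls by r x L and the mean baseline by 0.5 x L. Adjusting for baseline with slope about 0.5 returns 0.25 x L. That arm's adjusted mean is therefore too low (too good) by about L(p) x (r - 0.25).

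For p = 5%: L = 0.1031/0.95 = 0.1086, giving 0.027, 0.038 and 0.049 at the three values of r. For p = 2%: L = 0.0484/0.98 = 0.0494, giving 0.012, 0.017 and 0.022.

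**Simulation check.** With 4,000,000 simulated per arm, month 6 was regressed on arm and baseline among those retained. In large samples this is equivalent to imputing from arm and baseline and then fitting the planned model. True effect 0.20:

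| Loss, control / intervention | r = 0.5 | r = 0.6 | r = 0.7 |
|---|---|---|---|
| 1% / 0% | 0.194 | 0.191 | 0.188 |
| 2% / 0% | 0.188 | 0.182 | 0.178 |
| 5% / 0% | 0.173 | 0.161 | 0.150 |
| 5% / 3.3% (one shared cut-off) | 0.193 | 0.188 | 0.185 |
| 5% / 5% | 0.201 | 0.200 | 0.200 |
| 1% / 3% | 0.212 | 0.216 | 0.220 |
| 2% / 5% | 0.216 | 0.221 | 0.228 |

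The formula agrees: for 5% / 0%, 0.20 less 0.027, 0.038 or 0.049 is 0.173, 0.162 or 0.151.

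**Consequences for testing.**
- At 5% / 0%, single-test power at 0.05 falls from 96% to 80-90%.
- With no true effect and 5% / 0%, the estimate is -0.03 to -0.05. A significant result favouring control occurs in about 7-15% of trials at 0.05 (nominal 2.5%), or 1-3% at 0.005, the first step of the plan's multiplicity procedure (nominal 0.25%).
- With no true effect and 2% / 5%, a significant result favouring the intervention occurs in 5-7.5% at 0.05, or 0.6-1.1% at 0.005.

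These figures are for outcomes adjusted for baseline. PoC-OP has no baseline covariate, and its bias was not modelled.

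**The case against.** The strongest reply is that section VI already answers the point. It speaks of leaving the control group, not the study, and the promise of assessments for all enrolled participants follows almost at once. The same section adds contact escalation up to home visits, and the model uses the randomised arm. That stands for section VI. A reader might infer that severe controls are dropped from follow-up or analysis under that rule; the documents do not support this reading.

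Section VIII.A can also be read mildly. One sentence is a safety guarantee, another describes a pause with return, and two severe scores lead to monitoring and a referral decision, not to removal. The discretionary wording on continuing in the study still leaves the matter open. The section also announces removal criteria with no list after the sentence. A reader might infer that none were written, but the list may have been lost when the text was extracted, so nothing here rests on it.

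A reader might also infer bias in favour of the intervention, because its participants may be checked more often. The support is thin. The only rule that names an arm names control, the usual-care calls are meant to mirror the intervention schedule, and other passages say biweekly for both arms.

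The size is fairly challenged too. Removal is a judgement. The section VI criteria, read literally, mostly need Paykel 4 or 5, and current suicidal risk is excluded at entry. If 5% of controls meet the cut but only half are lost, the estimate is 0.175-0.186; if a quarter, 0.188-0.194. With r = 0.3, full 5% loss gives 0.195. If referral itself improves outcomes by 0.5 SD, following everyone gives about 0.175 and losing 5% of controls gives 0.15-0.17, so the bias shrinks to 0.003-0.025. All of this stands and limits the size of the point, not its existence.

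**Conclusion.** The concern holds in a conditional form. The live problem is the study-level wording in section VIII.A, which conflicts with section VI's unqualified promise of follow-up. If it is applied so that assessments stop, outcomes go missing because of post-baseline severity that the planned imputation does not contain. The bias is toward the null if more severe controls are lost, and away from it in the less well-supported case that more severe intervention participants are lost. There is none if losses are equal or if assessments continue.

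The likely size is modest. At 1-2% control-only loss the shift is at most about 0.02, or 0.4 of a standard error (0.022/0.0536). At 5% it is 0.03-0.05. These values rest on assumed correlations, assumed removal rates and loss of everyone above the cut. The documents establish the ambiguity, not an actual bias. It should be fixed because the remedy is cheap and the planned imputation could not repair the loss afterwards. Confidence is medium.

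**What to change.** In sections VI and VIII.A, state that:
- referral or removal for severity ends only arm-specific contacts (usual-care calls or CHW sessions);
- every randomised participant in either arm who has not withdrawn consent keeps the month 3, 6 and 12 assessments and is analysed as randomised, whether or not referred;
- the date and reason of each referral or removal are recorded, and the counts are reported by arm.

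Clinical thresholds, emergency procedures and referrals do not change. The section VII.B imputation can stay as it is, because the change prevents the loss.

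The cost is a wording change and one date-and-reason field. The interviews, contact escalation and gift cards are already planned for enrolled participants in sections V and VI. The downside is a few harder follow-up contacts with people in specialty or emergency care.

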Data will be collected at several points. All potential participants will complete a 20-30-minute screener to determine eligibility. Eligible participants will then complete a baseline assessment, as well as follow-up assessments at 3, 6 and 12 months post-baseline. In addition, all participants will complete a biweekly symptom assessment, using the PHQ-9 and GAD-7, and the Paykel Suicide Screener, if necessary.

VII. Biostatistical Analysis

A. Specific data variables being collected for the study (e.g. data collection sheets).

Screener, Baseline Assessment, Follow-up Assessment, Symptom Assessment (PHQ-9 and GAD-7)

The proposed study has four goals:

- 1) To test the effectiveness of an evidence-based, CHW-led mental health intervention, The Strong Minds-Strong Communities Randomized Clinical Trial (RCT), focused on (1)

decreasing depression and anxiety symptoms, (2) improving functioning, and (3) increasing perceived quality of care among low-income racial, ethnic, and linguistic minorities.

- 2) To test whether there is a differential effect of Strong Minds-Strong Communities based on participants' race and ethnicity, thereby identifying whether the intervention can be particularly effective for certain racial and ethnic groups.
- 3) To test whether there is a differential effect of Strong Minds-Strong Communities based on participants' language, thereby identifying whether the intervention can be particularly effective for certain linguistic groups.
- 4) To test whether there is a differential effect of Strong Minds-Strong Communities in North Carolina compared to Massachusetts, thereby identifying whether the effectiveness of the intervention is associated with a specific geographic location.

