Moderators. In Goal 2, race and ethnicity will be used as a moderator of the main independent variable (intervention condition). Using self-reported information, participants will be classified into four mutually exclusive categories: Latinx, non-Latinx Black, Asian, and non-Latinx White. In Goal 3, language will be used as a moderator of the main independent variable (intervention condition). Using self-reported information, participants will be classified into four mutually exclusive categories: English, Spanish, Mandarin, and Cantonese. In Goal 4, the site of recruitment will be used as a moderator of the intervention condition. Participants will be classified into two mutually exclusive categories of place of residence: North Carolina or Massachusetts.

Endpoints. The primary endpoints will be change from baseline in depression and anxiety symptoms, level of functioning, and perceived quality of care at month 6 (end of intervention) and at month 12 (6-months post-intervention). The key secondary effectiveness endpoints will

be the change from baseline in the score on the CAT-MH depression (range 0 to 100 with higher scores indicating worse depression symptoms) and the CAT-MH anxiety (range 0 to 100 with higher scores indicating worse anxiety symptoms) at month 6 and 12. The primary and key secondary effectiveness endpoints will be also evaluated in prespecified subgroup analyses based on participant's race and ethnicity, language, and site. Other exploratory endpoints will include changes from baseline in HSCL-25, WHODAS 2·0, PoC-OP, CAT-MH depression, and CAT-MH anxiety scores at month 3, about midway through the intervention. Finally, the primary and key secondary effectiveness endpoints will be evaluated in exploratory subgroup analyses based on the participant's baseline severity of depression and anxiety.

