Prespecified subgroup analyses of the primary and key secondary endpoints will be performed for participant's self-identified race and ethnicity (non-Hispanic White, non-Hispanic Black, Asian, and Hispanic or Latino), language (English, Spanish, Mandarin, and Cantonese), and site (Massachusetts and North Carolina). Subgroup differences will be tested in three omnibus interaction tests. These three interactions will be examined for 5 outcome scores (HSCL-25, WHODAS 2·0, PoC-OP, CAT-MH anxiety, and CAT-MH depression) at month 6 and month 12, which will result in 30 statistical tests ($3 \times 5 \times 2$). No adjustment for the multiple comparisons will be made, and about two statistically significant interaction tests ($P < 0.05$) are expected on the basis of chance alone.

Change from baseline in HSCL-25, WHODAS 2·0, PoC-OP, CAT-MH depression, and CAT-MH anxiety scores at the exploratory endpoint at month 3, and exploratory subgroup analyses based on participant's baseline severity of depression and anxiety will similarly be analyzed using a general linear model which included baseline scores (except for PoC-OP) and site as covariates.

B. Missing data

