We will conduct analysis of missing data at either endpoint (primary or exploratory) to test whether that, conditional on the observed baseline variables (including baseline outcome scores), the missing at random assumption is plausible. Missing data for all statistical models (primary and key secondary endpoints, exploratory endpoint, prespecified subgroup analyses and exploratory subgroups analyses) will be handled using model-based imputation. For example, missing values to analyze change from baseline in HSCL-25 scores at the 6-month endpoint will be imputed using a general linear model where HSCL-25 scores at month 6 will be the dependent variable. An effect coded variable for intervention condition, HSCL-25 scores at baseline, and a binary indicator for site (Massachusetts versus North Carolina) will be included as predictors. The model further will also include the auxiliary baseline variables associated with missingness (e.g., participant's age or gender). The same model-based imputation will be employed for all primary and key secondary endpoints, and the exploratory endpoint. Imputation models for subgroup analyses (prespecified and exploratory) will add the moderator and its interaction with intervention condition as predictors. For each model, 20 imputed datasets will be generated. Analyses of imputed data will use Rubin's rules to obtain pooled estimates and their standard errors.

C. Power Analysis (e.g., sample size, evaluable subjects, etc.)

The proposed study aimed to recruit 1,200 participants equally distributed across sites (North Carolina and Massachusetts) and intervention conditions (Intervention and Control). That is $N = 600$ intervention participants (300 in North Carolina and 300 in Massachusetts) and $N = 600$ enhanced usual care participants (300 in North Carolina and 300 in Massachusetts).

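### The language and race/ethnicity moderators very probably overlap but are tested in separate models, so a language interaction could not be attributed to language rather than ethnicity

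*Combined protocol and SAP*

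**What the plan says.** Section VII.A of the combined protocol and SAP lists four goals. Goal 2 asks whether the effect differs by race and ethnicity. Goal 3 asks the same about language, "thereby identifying whether the intervention can be particularly effective for certain linguistic groups". The Moderators paragraph gives each goal one moderator. Race/ethnicity has four levels, and for language "participants will be classified into four mutually exclusive categories: English, Spanish, Mandarin, and Cantonese".

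The Statistical Analyses paragraphs then state: "Subgroup differences will be tested in three omnibus interaction tests". The three moderators are race/ethnicity, language and site, each examined for five outcomes at two visits. That makes 30 tests, with no multiplicity adjustment and a remark on how many would be significant by chance. The missing-data section (VII.B) adds a single moderator and its interaction with arm to each subgroup imputation model.

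The power section (VII.C) gives the ethnic mix as "roughly 63% Latinx, 14% non-Latinx Black, 13% Asian, 9% White, and 1% other races or ethnicities". It gives no language mix, no language-by-ethnicity table and no power for the language test. Nowhere does the plan put both interactions in one model, compare languages within an ethnic group, or caution that the two moderators overlap.

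**The concern.** Goals 2 and 3 are presented as two questions, but the groups compared are probably much the same people. Eligibility (section III.A) admits speakers of English, Spanish, Mandarin or Cantonese. It is reasonable to assume that Spanish speakers are mostly Latinx, that Mandarin and Cantonese speakers are mostly Asian, and that Black and White participants are nearly all in the English group. The Spanish-versus-English comparison then also compares Latinx participants with a group rich in Black and White participants. Randomisation does not remove this. It balances the arms within each language group, but it does not balance ethnicity between language groups.

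Two misreadings follow. A difference in benefit between ethnic groups could be reported as the programme working better in a particular language, which could misdirect decisions on language-specific delivery. And one underlying signal could be counted twice, as a finding under Goal 2 and again under Goal 3. The chance-findings remark in the plan concerns multiplicity and does not cover this.

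**Working it through.** **Inputs from the documents (VII.C).** 1,200 randomised 1:1, with 13% nonparticipation. The effective size reproduces: 1,200 × 0.87 = 1,044 ("from North Carolina and Massachusetts is thus effectively 1044"). The stated 87% power is for the overall effect of 0.20 SD and is not used here. Removing the 1% of other ethnicity leaves 0.99 × 1,044 ≈ 1,034: Latinx 658, Black 146, Asian 136, White 94.

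**Assumptions.** A share p of Latinx participants use Spanish and the same share of Asian participants use Mandarin or Cantonese, with p = 60%, 80% or 95%. Everyone else uses English. Outcome SD is 1 and arms are 1:1 in every cell. Effects depend on ethnicity only, so there is no language effect once ethnicity is held fixed.

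**Method.** A subgroup effect in n participants has variance 4/n. The omnibus language-by-arm test has 3 df and noncentrality λ = Σ (n_g/4)(d_g − d̄)². Its rejection rate is the noncentral chi-square probability above the 5% critical value, 7.81.

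**Worked case, p = 80%, effects 0.4 (Latinx, Asian) and 0.1 (Black, White).**
- English group: 658 × 0.2 + 136 × 0.2 + 146 + 94 ≈ 399. Its mean effect is (0.4 × 159 + 0.1 × 240)/399 ≈ 0.219.
- Non-English group: 1,034 − 399 = 635, effect 0.4.
- Apparent Spanish-minus-English difference: 0.4 − 0.219 = 0.181.
- Because all non-English groups share one effect, λ = ¼ × (635 × 399/1,034) × 0.181² ≈ 2.0. The rejection rate is about 19%.

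**Other cases.** Apparent Spanish-minus-English difference in SD, then rejection rate:

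| Effects | p = 60% | p = 80% | p = 95% |
|---|---|---|---|
| Latinx/Asian 0.4, Black/White 0.1 | 0.13; 12% | 0.18; 19% | 0.26; 31% |
| Latinx/Asian 0.5, Black/White 0 | 0.21; 27% | 0.30; 48% | 0.43; 73% |
| Inside VII.C bands: White 0.55, Black 0.25, Latinx/Asian 0.40 | 0.01; 5% | 0.02; 5% | 0.03; 5% |
| Inside bands: White 0.55, Black 0.15, Latinx 0.45, Asian 0.35 | 0.07; 7% | 0.09; 9% | 0.13; 11% |
| Inside bands: White 0.51, Black 0, Latinx/Asian 0.49 | 0.12; 12% | 0.17; 18% | 0.25; 29% |

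In the third row the White and Black effects nearly cancel within the English group. In the last row they do not.

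**With ethnicity-by-arm also in the model**, the language test rejects 5% of the time under a pure ethnicity effect, as it should. The price is power. For a pure language effect (0.4 in non-English speakers, 0.1 in English speakers), power falls from 51%, 49% and 41% for language alone to 39%, 27% and 11% for language adjusted for ethnicity, at p = 60%, 80% and 95%.

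**Precision of within-ethnicity contrasts.** SE = √(4/n_nonEnglish + 4/n_English).
- Latinx, n = 658. At 60%: √(4/395 + 4/263) = 0.16. At 95%: √(4/625 + 4/33) = 0.36. The difference detectable with 80% power is about 2.8 × SE, or 0.45 to 1.0 SD.
- Asian, n = 136. At 60%: √(4/81 + 4/54) = 0.35. At 95%, with about 7 English speakers, the SE is 0.79. Detectable differences are about 0.98 to 2.2 SD.

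**The case against.** The strongest reply is that Goal 3 can be read descriptively: do average effects differ between language groups? On that reading the planned test is valid. In the scenarios above the group averages really do differ, so its null hypothesis is false. A reader might infer that 12% to 31% is a false-positive rate to be set against 5%. The documents do not support that. These rates are the power of the test to detect a real difference between language groups, and the difficulty lies only in what that difference is attributed to. This part of the objection stands.

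A reader might also infer that language is fully nested in ethnicity and that the trial cannot separate the two. The documents give no language counts, and English can occur in all four ethnic groups. A contrast within Latinx participants can be estimated if English-speaking Latinx participants enrol. The gap is in the analysis plan and does not follow from the design.

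It is also fair to say that the first two effect patterns in the table put White participants lowest, whereas VII.C assumes they benefit most, and that one pattern inside the plan's bands leaves the rate at 5%. But other patterns inside the same bands reach 11% and 29% at p = 95%, so the plan's assumptions do not rule the problem out.

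Finally, within-ethnicity contrasts are imprecise and add to 30 unadjusted tests. That is a good reason not to make every statement about language depend on them. It does not make the one-moderator result attributable to language.

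**Conclusion.** The point holds as a limit on interpretation. The planned language test can show that effects differ between language groups. It cannot show that language, as distinct from ethnicity, is the reason, and no other planned analysis fills that gap. One signal may therefore appear under both Goal 2 and Goal 3.

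The size depends on two things the documents do not fix: the language split (assumed 60% to 95% non-English among Latinx and Asian participants) and the pattern of effects by ethnicity. The rejection rate is about 12% to 31% for effects of 0.4 versus 0.1 SD. It runs from about 5% to 29% across the patterns tried inside the plan's own bands, which are examples and not bounds. The overall treatment comparison is unaffected.

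**What to change.** Keep the three omnibus tests and change the SAP as follows:

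- Report a language-by-ethnicity table by arm.
- For each outcome and visit, add one exploratory model with both ethnicity-by-arm and language-by-arm terms (5 × 2 = 10 models).
- Add an exploratory Spanish-versus-English contrast of the intervention effect within Latinx participants. Do the same within Asian participants only if the table shows enough English speakers.
- Report these as estimates with confidence intervals, and do not count them as further significance tests.
- Put the matching terms in the subgroup imputation models, which at present carry one moderator each.
- State that a result seen only in the one-moderator test will be described as a difference between combined ethnicity-language groups.

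The cost is SAP wording and a few more models on data already collected. The downside is low precision: SE about 0.16 to 0.36 SD within Latinx and 0.35 to 0.79 SD within Asian participants at 60% to 95% non-English. The added analyses therefore qualify how the planned test is read and do not replace it. A wide interval means the question of language versus ethnicity stays open, and it should not be read as evidence that language has no role.
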